14.3.5	Displays of Laboratory Results	107
14.3.6	Displays of Vital Signs	126
14.4	Summary of Concomitant Medications	130
	APPENDIX 2. FIGURE MOCK-UPS	131
10.1	Disposition of Subjects	134
14.2	Efficacy/Immunogenicity Data.....	135
14.2.2	Efficacy/Immunogenicity Response Figures by Measure, Treatment/Vaccination, and Time Point.....	135
14.3	Safety Data.....	140

Table of Contents (continued)

14.3.1 Adverse Events	140
14.3.5 Displays of Laboratory Results	147
APPENDIX 3. LISTINGS MOCK-UPS.....	149
APPENDIX 4. NCA TEMPLATE.....	170

LIST OF ABBREVIATIONS

ADCC	Antibody-Dependent Cellular Cytotoxicity
AE	Adverse Event
ALT	Alanine Aminotransferase
ATC	Anatomical Therapeutic Classification
BP	Blood Pressure
BMI	Body Mass Index
CI	Confidence Interval
CRF	Case Report Form
CSR	Clinical Study Report
DMID	Division of Microbiology and Infectious Diseases, NIAID, NIH
eCRF	Electronic Case Report Form
ELISA	Enzyme-linked Immunosorbent Assay
FDA	Food and Drug Administration
GLA-SE	Glucopyranosyl Lipid Adjuvant Stable oil-in-water Emulsion
GMFR	Geometric Mean Fold Rise
GMT	Geometric Mean Titers
HCV	Hepatitis C Virus
ICH	International Conference on Harmonisation
ICS	Intracellular Cytokine Staining
IM	Intramuscular
LLOQ	Lower Limit of Quantification
MAAE	Medically Attended Adverse Events
MedDRA	Medical Dictionary for Regulatory Activities
miITT	Modified Intention to Treat
MOP	Manual of Procedures
N	Number (refers to number of subjects)
NIH	National Institutes of Health
NOCMC	New Onset Chronic Medical Condition
PBMC	Peripheral Blood Mononuclear Cell
PI	Principal Investigator
PIMMC	Potentially Immune-Mediated Medical Condition
PP	Per Protocol

List of Abbreviations (continued)

PT	Preferred Term
RCD	Reverse Cumulative Distribution
SAE	Serious Adverse Event
SAP	Statistical Analysis Plan
SD	Standard Deviation
SDCC	Statistical and Data Coordinating Center
SMC	Safety Monitoring Committee
Sm-p80	S. mansoni Caplain Protein with a mass of approximately 80 kDa
SOC	System Organ Class
ULN	Upper Limit of Normal
ULOQ	Upper Limit of Quantification
WBC	White Blood Cell
WFI	Water-For-Injection
WHO	World Health Organization

1. PREFACE

The Statistical Analysis Plan (SAP) for “A Phase 1, Open-Label, Dose-Escalation Trial to Evaluate the Safety, Reactogenicity, and Immunogenicity of Sm-p80 + GLA-SE (SchistoShield®) Vaccine in Healthy Adults” (DMID Protocol 18-0018) describes and expands upon the statistical information presented in the protocol.

This document describes all planned analyses and provides reasons and justifications for these analyses. It also includes sample tables, listings, and figures planned for the final analyses. Regarding the final analyses and Clinical Study Report (CSR), this SAP follows the International Conference on Harmonization of Technical Requirements for Registration of Pharmaceuticals for Human Use (ICH) Guidelines, as indicated in Topic E3 (Structure and Content of Clinical Study Reports), and more generally is consistent with Topic E8 (General Considerations for Clinical Trials) and Topic E9 (Statistical Principles for Clinical Trials). The structure and content of the SAP provides sufficient detail to meet the requirements identified by the FDA and ICH, while all work planned and reported for this SAP will follow internationally accepted guidelines published by the American Statistical Association and the Royal Statistical Society for statistical practice.

This document contains four sections: (1) a review of the study design, (2) general statistical considerations, (3) comprehensive statistical analysis methods for efficacy and safety outcomes, and (4) a list of proposed tables and figures. Within the table, figure, and listing mock-ups ([Appendix 1](#), [Appendix 2](#), and [Appendix 3](#), respectively), references to CSR sections are included. Any deviation from this SAP will be described and justified in protocol amendments and/or in the CSR, as appropriate. The reader of this SAP is encouraged to also review the study protocol for details on conduct of the study and the operational aspects of clinical assessments.

2. INTRODUCTION

In preclinical and safety studies, Sm-p80-based vaccines provided comprehensive coverage against different stages of the parasite's life cycle, including its eggs, schistosomula, and adult worms. Sm-p80 is unique in that it has demonstrated desirable outcomes of Sm-p80 vaccination including: 1) prophylactic efficacy against *S. mansoni* (intestinal/hepatic schistosomiasis); [9] 2) reduction in egg-induced tissue/organ pathology; [9] 3) post-exposure therapeutic efficacy by elimination of established adult worms in chronic disease[11] 4) cross species-protection against *S. haematobium* (urinary schistosomiasis) [12] and *S. japonicum* (Asiatic/oriental disease); [13] 5) long lived immunity as Sm-p80 specific IgG titers are present in mice for up to 60 weeks and 5-8 years in baboons; [14] and 6) maternal transfer of Sm-p80-specific antibodies in baboons. [14] Sm-p80-specific IgE has not been detected in high-risk or infected populations from Africa and South America, thus reducing the possibility of hypersensitivity following vaccination with the Sm-p80 vaccine in humans. The protective immune response to *Schistosoma* is thought to be antibody mediated with cell-mediated help to skew the antibody isotypes to IgG1 and IgG3.

The 5 µg dose of GLA-SE to be used in this trial is comfortably in the mid-range of tested doses of the adjuvant and has been shown to be safe and well tolerated in hundreds of human subjects. As reported in the GLA-SE Investigator Brochure (v5, March 2016) many preclinical and nonclinical studies in mice, guinea pigs, rats, rabbits, and non-human primates have demonstrated the immunostimulatory properties of GLA-SE with no significant safety signals. GLA-SE has also been evaluated in numerous completed and ongoing clinical trials. These trials have investigated GLA-SE formulated with antigens, including recombinant antigens, developed for vaccines against a wide variety of diseases, including leishmaniasis, [15] tuberculosis, [16, 17] influenza, [18, 19] schistosomiasis, [20] and malaria. These clinical trials have evaluated GLA-SE at 0.5, 1, 2, 2.5, 5, 10, or 20 µg dose levels. In these studies, over 1100 subjects have received at least one study injection containing GLA-SE. Safety data have not revealed any significant safety issues at any dose level tested. Reactions to vaccines varied from study to study, but were generally mild, resolved quickly, and typical of vaccinations by the IM route.

In the GLP-toxicity study of SchistoShield®, there were no findings definitively attributed to systemic toxicity of Sm-p80 with or without GLA-SE. This study indicated that the SchistoShield® vaccine is safe and well tolerated in rabbits when administered IM for up to four injections at the highest proposed human dose of Sm-p80 antigen given with GLA-SE. No significant local or systemic toxicity was found. A general safety assessment of SchistoShield® vaccine in baboons also indicated that the vaccine is safe and well tolerated for up to the highest dose of 250 µg of Sm-p80 and 50 µg of GLA-SE, further supporting the observation from the GLP-toxicity study in rabbits. Based on the N+1 rule, the GLP-toxicity study in rabbits supports the use of SchistoShield® vaccine in the first-in-human clinical trial for up to three injections at the high dose of 100 µg Sm-p80.

The promising results of the preclinical evaluations and the urgent need for an effective schistosomiasis vaccine support advancement of the SchistoShield® vaccine candidate to an initial Phase 1 human trial in healthy volunteers in the United States.

2.1. Purpose of the Analyses

The purpose of this trial is to determine the safety, reactogenicity, and immunogenicity in 45 healthy adult subjects of the candidate investigational schistosomiasis vaccine: Sm-p80 (10 µg, 30 µg, and 100 µg) adjuvanted with 5 µg of GLA-SE adjuvant. The analyses will also assess the necessity of the adjuvant by comparison of the previous doses to 100 µg Sm-p80 only (Table 1). Subjects will receive three IM injections

of 0.5 mL of the designated study product formulation, on Days 1, 29, and 57 (28 days apart) or on a delayed booster dose schedule on Days 1, 29, and 180.

The protocol for DMID 18-0018 calls for a planned interim analysis on safety data and immunogenicity assays, including total IgG Enzyme-linked Immunosorbent Assay (ELISA), at the discretion of the study team prior to completion of follow-up of all subjects.

3. STUDY OBJECTIVES AND ENDPOINTS

3.1. Study Objectives

3.1.1. Primary

- To assess the safety and reactogenicity following receipt of three doses of the following
 - Group A: 100 µg Sm-p80 (unadjuvanted)
 - Group B: 10 µg Sm-p80 + 5 µg GLA-SE
 - Group C: 30 µg Sm-p80 + 5 µg GLA-SE (delayed booster)
 - Group D: 30 µg Sm-p80 + 5 µg GLA-SE
 - Group E: 100 µg Sm-p80 + 5 µg GLA-SE

with Groups A, B, D, and E administered intramuscularly on Days 1, 29, and 57 and Group C administered on Days 1, 29, and 180.

3.1.2. Secondary

- To assess anti-Sm-p80 IgG antibody responses from samples collected at specified time points.

3.1.3. Exploratory

- To assess innate and adaptive immune signatures from samples collected at specified time points.

3.2. Study Endpoints or Outcome Measures

3.2.1. Primary

- Occurrence of study vaccine-related SAEs from the time of the first study vaccination through approximately 12 months after the last study vaccination
- Occurrence of solicited injection site and systemic reactogenicity events from the time of each study vaccination through 7 days after each study vaccination
- Occurrence of clinical safety laboratory AEs from the time of each study vaccination through approximately 28 days after each study vaccination
- Occurrence of all unsolicited AEs, regardless of the assessment of seriousness or relatedness, from the time of each study vaccination through 28 days after each study vaccination
- Occurrence of SAEs, MAAEs, NOCMCs, and PIMMCs from the time of the first study vaccination through approximately 12 months after the last study vaccination

3.2.2. Secondary

- For Sm-p80 IgG antibodies, number of subjects achieving seroconversion, defined as fourfold rise from baseline, at approximately 28 days after the first, second, and third study vaccinations
- Geometric mean titers of serum Sm-p80 IgG antibodies from samples collected at 7 and 28 days after each vaccination, and at 124 days after the last vaccination

3.2.3. Exploratory

- Identification and characterization of gene expression changes as measured using RNA-seq analysis from whole blood relative to last vaccination
 - Days 8 and 29 vs. Day 1, and Day 36 vs. Day 29 for all study groups
 - Day 57 vs. Day 29, Day 64 vs. Day 57 for Groups A, B, D, and E
 - Day 187 vs. Day 180 for Group C
- Identification and characterization of gene expression changes as measured using RNA-seq relative to last vaccination that correlate with peak Sm-p80 IgG antibody levels
 - Days 8 and 29 vs. Day 1, and Day 36 vs. Day 29 for all study groups
 - Day 57 vs. Day 29, Day 64 vs. Day 57 for Groups A, B, D, and E
 - Day 187 vs. Day 180 for Group C

3.3. Study Definitions and Derived Variables

Seroconversion is defined as a fourfold rise from baseline.

Clinical laboratory evaluations, vital signs, reactogenicity, and immunogenicity will be assessed on the day of, prior to the first study product injection (Day 1) to establish baseline. If a single ELISA result is below the lower limit of quantification (LLOQ) or above the upper limit of quantification (ULOQ) then the result will be imputed as LLOQ or ULOQ, respectively. If both ELISA results are below LLOQ, then the value will be imputed as $\frac{1}{2} \times \text{LLOQ}$. If both ELISA results are above ULOQ, then ULOQ will be reported.

Any medical condition that is present at the time that the subject is screened will be considered baseline and not reported as an AE. However, if the existing severity of any pre-existing medical condition increases, it will be recorded as an AE.

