## **2.2.2 Study Population**

The study population will include 45 healthy adults 18 through 55 years of age, inclusive, who have no prior exposure to schistosomes and have no history of treatment for schistosomiasis. The study population will be drawn from the membership of the Kaiser Permanente Washington health plan and from the population of the greater Seattle, Washington area and will exclude women who are pregnant or who are breast feeding a child.

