4. INVESTIGATIONAL PLAN

4.1. Overall Study Design and Plan

This is a Phase 1, open label, dose-escalation clinical trial to evaluate the safety, reactogenicity, and immunogenicity of Sm-p80 + GLA-SE candidate schistosomiasis vaccine (SchistoShield®) in healthy adults 18 through 55 years of age. The Sm-p80 antigen is a recombinant protein produced in *E. coli* and GLA-SE is an immunological adjuvant.

Five treatment groups, each including nine subjects, will receive three intramuscular (IM) injections of 0.5 mL of designated study product on either Days 1, 29, and 57 or on Days 1, 29, and 180. Group A (unadjuvanted comparator) will receive 100 µg Sm-p80 alone on Days 1, 29, and 57; Group B (low dose standard schedule) will receive 10 µg Sm-p80 + 5 µg GLA-SE on Days 1, 29, and 57; Group C (mid dose delayed booster) will receive 30 µg Sm-p80 + 5 µg GLA-SE on Days 1, 29, and 180; Group D (mid dose standard schedule) will receive 30 µg Sm-p80 + 5 µg GLA-SE on Days 1, 29, and 57; Group E (high dose standard schedule) will receive 100 µg Sm-p80 + 5 µg GLA-SE on Days 1, 29, and 57. Dose escalation will proceed as described in the Protocol Summary (protocol v2.0).

Reactogenicity will be measured by the occurrence of solicited injection site and systemic reactions from the time of each study product injection through seven days after each study product injection. Unsolicited AEs of all severities, and concomitant medications, will be collected from the time of each study product injection through the next 28 days. During period of follow-up outside of the 28-day post-vaccination interval, only SAEs, medically attended adverse events (MAAEs), new onset chronic medical conditions (NOCMCs), and potentially immune-mediated medical conditions (PIMMCs) will be collected. Clinical laboratory evaluations for safety will be performed on venous blood collected prior to, and approximately seven days after, each study vaccination.

Immunogenicity testing will include measuring titers of total IgG against the Sm-p80 protein by ELISA. Gene expression will be evaluated using RNA Seq analysis from whole blood.

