11. IMMUNOGENICITY

11.1. Secondary Immunogenicity Analysis

11.1.1. ELISA (anti Sm-p80 Total IgG)

Antibody responses, measured by total IgG production to the recombinant Sm-p80 protein using ELISA will be presented at baseline (Day 1) and by study day (Days 8, 29, 36, 57 for all treatment groups; additionally Days 64, 85, 181 for Groups A, B, D, and E, and Days 180, 187, 208, 304 for Group C) using descriptive statistics in [Table 15](#) (mITT immunogenicity population). For post-baseline timepoints, geometric mean fold rise (GMFR) and the proportion of subjects with at least a 4-fold rise will be presented with 95% confidence intervals for mITT population in [Table 16](#) (mITT immunogenicity population). The ELISA seroresponse (at least 4-fold rise) rates at 28-days post vaccination will be compared between Group A vaccine group and each treatment group using Fisher's Exact Test ([Table 17](#)). Confidence intervals for proportions are calculated using Wilson Score methodology without continuity correction. Confidence intervals calculated for GMT and GMFR follow a t-distribution.

Antibody responses will be adjusted for baseline. Reverse cumulative distributions (RCD) curves will be presented with separate panels for each timepoint for mITT population in [Figure 2](#). Graphs of Geometric Mean Anti-Sm-p80 ELISA responses over time will be presented in [Figure 3](#). Individual time trends for each Anti-Sm-p80 ELISA will be presented in [Figure 4](#).

Results of individual total IgG immunogenicity responses, scheduled and unscheduled, will be presented in [Listing 9](#).

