14.2 Immunogenicity Data

Table 15: Anti-Sm-p80 ELISA Total IgG Geometric Mean Titers (GMT) Results with 95% Confidence Intervals by Time Point and Treatment Group, mITT Immunogenicity Population

Time Point	Statistic	Group A: 100 µg Sm-p80 (unadjuvanted) (N=X)	Group B: 10 µg Sm-p80 + 5 µg GLA-SE (N=X)	Group C: 30 µg Sm-p80 + 5 µg GLA-SE (delayed booster) (N=X)	Group D: 30 µg Sm-p80 + 5 µg GLA-SE (N=X)	Group E: 100 µg Sm-p80 + 5 µg GLA-SE (N=X)
Study Day 1 (Pre-Dose 1) (Baseline)	n	x	x	x	x	x
	GMT (95% CI)	x.x (x.x, x.x)	x.x (x.x, x.x)	x.x (x.x, x.x)	x.x (x.x, x.x)	x.x (x.x, x.x)
	Mean	x.x	x.x	x.x	x.x	x.x
	Std. Dev.	x.x	x.x	x.x	x.x	x.x
	Median	x.x	x.x	x.x	x.x	x.x
	(Minimum, Maximum)	(x.x, x.x)	(x.x, x.x)	(x.x, x.x)	(x.x, x.x)	(x.x, x.x)
Study Day 8 (7 Days Post Dose 1)	n					
	GMT (95% CI)					
	Mean					
	Std. Dev.					
	Median					
	(Minimum, Maximum)					
Study Day 29 (28 Days Post Dose 1; Pre-Dose 2)	n					
	GMT (95% CI)					
	Mean					

Table 15: Anti-Sm-p80 ELISA Total IgG Geometric Mean Titers (GMT) Results with 95% Confidence Intervals by Time Point and Treatment Group, mITT Immunogenicity Population (Continued)

Time Point	Statistic	Group A: 100 µg Sm-p80 (unadjuvanted) (N=X)	Group B: 10 µg Sm-p80 + 5 µg GLA-SE (N=X)	Group C: 30 µg Sm-p80 + 5 µg GLA-SE (delayed booster) (N=X)	Group D: 30 µg Sm-p80 + 5 µg GLA- SE (N=X)	Group E: 100 µg Sm-p80 + 5 µg GLA-SE (N=X)
	Std. Dev.					
	Median					
	(Minimum, Maximum)					
Study Day 36 (7 Days Post Dose 2)	n					
	GMT (95% CI)					
	Mean					
	Std. Dev.					
	Median					
	(Minimum, Maximum)					
Study Day 57 (Groups A, B, D, E: 28 Days Post Dose 2; Pre-Dose 3) (Group C: 28 Days Post Dose 2)	n					
	GMT (95% CI)					
	Mean					
	Std. Dev.					
	Median					
	(Minimum, Maximum)					
Study Day 64 (Groups A, B, D, E: 7 Days Post Dose 3)	n				N/A	

Table 15: Anti-Sm-p80 ELISA Total IgG Geometric Mean Titers (GMT) Results with 95% Confidence Intervals by Time Point and Treatment Group, mITT Immunogenicity Population (Continued)

Time Point	Statistic	Group A: 100 µg Sm-p80 (unadjuvanted) (N=X)	Group B: 10 µg Sm-p80 + 5 µg GLA-SE (N=X)	Group C: 30 µg Sm-p80 + 5 µg GLA-SE (delayed booster) (N=X)	Group D: 30 µg Sm-p80 + 5 µg GLA- SE (N=X)	Group E: 100 µg Sm-p80 + 5 µg GLA-SE (N=X)
	GMT (95% CI)			N/A		
	Mean			N/A		
	Std. Dev.			N/A		
	Median			N/A		
	(Minimum, Maximum)			N/A		
Study Day 85 (Groups A, B, D, E: 28 Days Post Dose 3)	n			N/A		
	GMT (95% CI)			N/A		
	Mean			N/A		
	Std. Dev.			N/A		

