	Median			N/A		
	(Minimum, Maximum)			N/A		
Study Day 180 (Group C: Pre-Dose 3)	n	N/A	N/A		N/A	N/A
	GMT (95% CI)	N/A	N/A		N/A	N/A
	Mean	N/A	N/A		N/A	N/A
	Std. Dev.	N/A	N/A		N/A	N/A
	Median	N/A	N/A		N/A	N/A
	(Minimum, Maximum)	N/A	N/A		N/A	N/A

Table 15: Anti-Sm-p80 ELISA Total IgG Geometric Mean Titers (GMT) Results with 95% Confidence Intervals by Time Point and Treatment Group, mITT Immunogenicity Population (Continued)

Time Point	Statistic	Group A: 100 µg Sm-p80 (unadjuvanted) (N=X)	Group B: 10 µg Sm-p80 + 5 µg GLA-SE (N=X)	Group C: 30 µg Sm-p80 + 5 µg GLA-SE (delayed booster) (N=X)	Group D: 30 µg Sm-p80 + 5 µg GLA- SE (N=X)	Group E: 100 µg Sm-p80 + 5 µg GLA-SE (N=X)
Study Day 187 (Group C: 7 Days Post Dose 3)	n	N/A	N/A		N/A	N/A
	GMT (95% CI)	N/A	N/A		N/A	N/A
	Mean	N/A	N/A		N/A	N/A
	Std. Dev.	N/A	N/A		N/A	N/A
	Median	N/A	N/A		N/A	N/A
	(Minimum, Maximum)	N/A	N/A		N/A	N/A
Study Day 181 (Groups A, B, D, E: 124 Days Post Dose 3)	n			N/A		
	GMT (95% CI)			N/A		
	Mean			N/A		
	Std. Dev.			N/A		
	Median			N/A		
	(Minimum, Maximum)			N/A		
Study Day 208 (Group C: 28 Days Post Dose 3)	n	N/A	N/A		N/A	N/A
	GMT (95% CI)	N/A	N/A		N/A	N/A
	Mean	N/A	N/A		N/A	N/A

Table 15: Anti-Sm-p80 ELISA Total IgG Geometric Mean Titers (GMT) Results with 95% Confidence Intervals by Time Point and Treatment Group, mITT Immunogenicity Population (Continued)

Time Point	Statistic	Group A: 100 µg Sm-p80 (unadjuvanted) (N=X)	Group B: 10 µg Sm-p80 + 5 µg GLA-SE (N=X)	Group C: 30 µg Sm-p80 + 5 µg GLA-SE (delayed booster) (N=X)	Group D: 30 µg Sm-p80 + 5 µg GLA- SE (N=X)	Group E: 100 µg Sm-p80 + 5 µg GLA-SE (N=X)
	Std. Dev.	N/A	N/A		N/A	N/A
	Median	N/A	N/A		N/A	N/A
	(Minimum, Maximum)	N/A	N/A		N/A	N/A
Study Day 304 (Group C: 124 Days Post Dose 3)	n	N/A	N/A		N/A	N/A
	GMT (95% CI)	N/A	N/A		N/A	N/A
	Mean	N/A	N/A		N/A	N/A
	Std. Dev.	N/A	N/A		N/A	N/A
	Median	N/A	N/A		N/A	N/A
	(Minimum, Maximum)	N/A	N/A		N/A	N/A

Note: N = Number of subjects in the mITT Immunogenicity Population; n = Number of subjects with results at the given time point. GMT = Geometric mean titer.

Pseudo Code:

```
/*Geometric Mean Titers*/
data dsn2;
  set dsn1;
  log_aval = log(aval);
proc means data=dsn2 n mean clm noint;
  by stdy trta;
  var log_aval;
  output out= gmt0(drop=_type_ _freq_)
    n= n
    mean= mean
    std= sd
    median= med
    max= max
    min= min
    lclm=lclm
    uclm=uclm;
data gmt;
  set gmt0;
  gmt = put(exp(mean),8.1); /*geometric mean titer*/
  gmt_l = put(exp(lclm), 8.1); /*lower bound*/

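### Where all or nearly all of a group's ELISA values are below LLOQ, the planned t-interval for GMT and GMFR narrows to little or no width and should not be printed as a 95% CI

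*SAP*

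**What the plan says.** SAP 3.3 handles unquantifiable results in two steps. If one duplicate is below LLOQ, that result becomes the LLOQ. For two low duplicates the rule is "If both ELISA results are below LLOQ, then the value will be imputed as" half the LLOQ, the same constant for every such subject.

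SAP 11.1.1 states that "Confidence intervals calculated for GMT and GMFR follow a t-distribution". The responses "will be presented at baseline (Day 1) and by study day", and Table 15 is titled "Anti-Sm-p80 ELISA Total IgG Geometric Mean Titers (GMT) Results with 95% Confidence Intervals by Time Point and Treatment Group". The Table 15 code logs each value, takes the mean and its t-limits, and exponentiates. It does not distinguish a substituted value from a measured one. The Table 16 code does the same with the fold rise.

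The design is "Five treatment groups, each including nine subjects", and Protocol 2.2.2 requires "no prior exposure to schistosomes". Under SAP 3.2.2 the GMT is a secondary endpoint at 7 and 28 days after each dose and at 124 days after the last.

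Neither document states the LLOQ, the expected share below it, a count of substituted values, or a rule for withholding an interval. SAP 6.5 concerns missing values only.

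**The concern.** Half LLOQ is an ordinary convention for a point value. The difficulty is the interval built on it. A t-interval takes its width from the spread of the data, and subjects who all receive the same constant contribute no spread. The fewer values the assay can measure, the narrower the interval becomes, which is the reverse of what a reader expects.

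Such cells are plausible. Subjects are unexposed by design, Protocol 2.1.3.2 reports no anti-Sm-p80 response in any baboon at Week 0, and Day 8 is only a week after the first exposure. Day 8 GMT is a secondary endpoint. Tables 15 and 16 and Figure 3 are in both interim packages (SAP 6.2), and SAP 6.6.2 allows those reports to be published and used by the product developers.

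**Working it through.** **Inputs from the documents.** n = 9 per group (SAP 4.1); substitution rule (SAP 3.3); log-scale t-interval (SAP 11.1.1, Table 15 code); two-sided 95%. The critical value on 8 df is 2.306.

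**Assumptions.** The documents give no LLOQ, share below LLOQ (f) or SD of log titre. Log10 titres are taken as normal with SD 0.2 to 0.8, and f is varied. Simulations used 100,000 samples of nine for SD 0.2 to 0.6 and 40,000 for SD 0.8.

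**1. The plan's own figure.** With nothing below LLOQ, the interval covers the true GMT in 94.9% to 95.0% of samples, so the nominal 95% reproduces.

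**2. All nine below.** The SD of the logs is 0, so the half-width is 2.306 × 0 / √9 = 0 and the interval is [0.5 LLOQ, 0.5 LLOQ]. If all nine are also below at Day 1, each fold rise is 0.5 LLOQ / 0.5 LLOQ = 1, and Table 16 prints 1.0 (1.0, 1.0).

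**3. How often this happens.** P(zero width) = f^9:

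| f | 50% | 75% | 90% | 95% | 99% |
|---|---|---|---|---|---|
| f^9 | 0.002 | 0.075 | 0.387 | 0.630 | 0.914 |

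Here f is the share of subjects with both duplicates below.

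**4. Coverage of the true GMT.**

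| f | SD 0.2 | SD 0.4 | SD 0.6 |
|---|---|---|---|
| 25% | 0.936 | 0.945 | 0.947 |
| 50% | 0.872 | 0.939 | 0.943 |
| 75% | 0.769 | 0.877 | 0.176 |
| 90% | 0.612 | 0.000 | 0.000 |
| 95% | 0.362 | 0.000 | 0.000 |

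At SD 0.8, coverage is 93% at 50% below. At SD 0.4 the median ratio of upper to lower limit falls from 3.9 with none below to 3.4 at 50%, 2.3 at 75%, 1.6 at 90% and 1.0 at 95%.

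**5. Bias separated from width.** The same intervals were scored against the mean of the substituted values. Coverage is then 0.93–0.94 at 50% below, 0.86–0.92 at 75%, 0.61 at 90% and 0.37 at 95%. At 90% and 95% this is almost exactly 1 − f^9 (1 − 0.387 = 0.613; 1 − 0.630 = 0.370), so the misses there are essentially the zero-width samples. The further fall in step 4, for example 0.176 against 0.858 at SD 0.6 and 75% below, is bias of the half-LLOQ value. It lies on average 1.85-fold above the true GMT in that case.

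**6. The SAP's duplicate rule.** With an assumed assay SD of 0.1 log10 and f now the share of single results below LLOQ, SD 0.4 gives coverage of 0.945, 0.867 and 0.000 at 50%, 75% and 90%. The pattern is the same.

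**7. A cut-off for withholding the interval.** P(fewer than 3 of 9 quantifiable) is the sum over k = 0, 1, 2 of C(9,k)(1−f)^k f^(9−k):

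- f = 50%: (1 + 9 + 36)/512 = 0.090
- f = 75%: 0.075 + 0.225 + 0.300 = 0.601
- f = 90%: 0.387 + 0.387 + 0.172 = 0.947

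Withholding whenever more than half are below would remove the interval in 50% of samples at f = 50%, where coverage is still 0.94 at SD 0.4.

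**The case against.** The strongest reply is that nothing in the documents shows these cells will occur. With no LLOQ and no expected share, a reader might infer from the mechanism that early-visit GMT intervals in general miss 95% coverage. The documents do not support that: with half or fewer below LLOQ the interval performs close to its nominal level at SD 0.4 and above. Nor do they place Day 29 among the affected visits, since vaccinated baboons had responded by Week 4 (Protocol 2.1.3.2). Protocol 2.1.5 says that unadjuvanted antigen gave lower titres in rabbits, not unquantifiable ones, so Group A is not shown to be affected either. These limits stand.

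A reader might also take the near-zero coverage figures as a measure of interval shrinkage. They are not; step 5 shows that much of the fall is bias in a point value that is kept.

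It could be said, too, that nothing is hidden. Table 15 prints SD, median, minimum and maximum, and Listing 9 and Figure 4 show individual values. With nine values, a median equal to the minimum reveals at least five substitutions, and an SD of 0 reveals complete collapse. That is largely right. What remains is that a cell with seven of nine below prints an ordinary-looking 95% interval, and no row states the count directly.

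Finally, the study is descriptive (SAP 6.8), and the seroconversion endpoint uses Wilson intervals, which do not collapse at 0 of 9. This limits the consequence but does not make a zero-width interval correct.

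**Conclusion.** The point holds conditionally and is minor. In any group and visit with all or nearly all values below LLOQ, the plan prints a 95% interval that is too narrow or has no width, for GMT and for GMFR. Day 1 and Day 8 are the plausible places, and of these only Day 8 is an endpoint visit. At 75% below, the interval is zero-width in 7.5% of samples; at 90%, in 39%; at 95%, in 63%. Those figures need only independence between subjects. The coverage figures also need the assumed log-normal titres and SDs. At half below or fewer the plan is adequate, except that coverage is 87% at half below if the SD is as small as 0.2 log10. No decision rule or test depends on these intervals.

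**What to change.** Keep half LLOQ as the point value. Then:

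- State the LLOQ in SAP 3.3.
- Add a row for n (%) below LLOQ, with the Wilson interval already used elsewhere in the SAP, to Tables 15 and 16. For nine of nine below, the lower limit is 9/(9 + 1.96²) = 70%, so the row reads 100% (70% to 100%).
- Add a sentence to SAP 11.1.1: the GMT or GMFR t-interval is printed as not estimable when few values are quantifiable (for example fewer than three of nine), and always when the SD is 0.
- Flag such points in Figure 3 as mostly below LLOQ, so that a missing bar is not read as precision.

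A censored-normal interval is not a full substitute at this sample size. In simulation at SD 0.4, fewer than two values were quantifiable in 29% of samples at 75% below and in 77% at 90%.

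The cost is one row in each of two tables, two short SAP additions and a figure note. The downside is that a few cells carry no t-interval, and the half-LLOQ bias in the point value remains, though the count row makes its extent visible.
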